10. PRIOR AND CONCOMITANT MEDICATION

The start and stop date, dose, unit, frequency, route of administration, and indication for all prior (taken within the 30 days prior to the screening visit) and concomitant (taken from the screening visit through the Follow-up Visit) medications and nondrug therapies (eg, blood transfusions, oxygen supplementation) received will be recorded.

In addition, all prior treatments for sarcoidosis administered since diagnosis will be recorded with start and stop date, dose, unit, frequency and route of administration to the extent of data availability.

10.1. Permitted Concomitant Medications

Subjects enrolled into the study must have been on stable prednisone dose for at least 4 weeks prior to Screening (Visit 1). Subjects who are treated with any disease modifying antisarcoidosis drugs (eg, methotrexate) must have been on a stable dose for at least 3 months prior to Screening (Visit 1). Corticosteroid tapering will be initiated as of Week 4 (Visit 3) according to the tapering algorithm described in [Section 7.2.4](#). The dose of all other antisarcoidosis medications should remain stable for the duration of the study. The dose may be reduced or discontinued only for toxicity but must not be increased.

10.2. Prohibited Concomitant Medications/Treatments

The following treatments will not be permitted during the study:

- No new antisarcoidosis medication is permitted.
- Treatment with antitumor necrosis factor- α (eg, infliximab, adalimumab) in the 3 months prior to Screening (Visit 1) and throughout the study.
- Administration of live or live-attenuated vaccines.
- Long acting corticotropins.
- Any investigational drug, device, or procedure administered as part of a research study.

If any prohibited medication is taken during the study, all pertinent information will be recorded in source documents and the eCRF. The designated study MM must be informed immediately so the sponsor may determine whether to continue the subject in the study.

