17. SUBJECT DISCONTINUATION OR WITHDRAWAL

17.1. Subject Withdrawal

Subjects who discontinue, or are withdrawn from the study for any reason, will be required to have the early termination safety and efficacy assessment procedures (Visit 8, see [Section 11.5](#)) as well as follow up procedures (Visit 12, see [Section 11.9](#)).

The reason for discontinuation will be recorded. A subject may be discontinued from the study for the following medical or administrative reasons:

Withdrawal by Subject

Subjects will be free to discontinue from the study at any time. Subjects who have received at least 1 dose of IMP but do not complete the study will not be replaced.

AE

If a dosed subject experiences an AE that, in the judgment of the investigator, sponsor or MM, presents an unacceptable consequence or risk to the subject, the subject will be discontinued from IMP. In addition, subjects who experience any of the AEs described in [Section 12.3.1](#) may have their dose reduced by 50% once or discontinued ([Section 17](#)).

Death

In the event that a subject dies during the study, death will be the reason for discontinuation.

Lost to Follow-up

Every effort should be made to maintain contact with subjects during their participation in the study. A subject may be considered lost to follow-up if there is no response to 3 attempts to reach the subject by telephone or electronically and no response to a certified letter sent to the last known address of the subject. Efforts to contact the subject should be noted in source documentation.

Met Withdrawal Criteria

Discontinuation from IMP is mandated if the subject becomes pregnant or receives live or live-attenuated vaccines.

Worsening of Disease Activity

Subjects may be withdrawn if, in the opinion of the investigator, there is a lack of efficacy during the study.

Other

If the above reasons are not applicable, please use the “Other” option and provide the appropriate reason for subject withdrawal.

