The significant protocol deviations will be summarized by category using frequency tabulations based on the safety population in the double-blind treatment phase and on open-label safety population in the open-label extension phase separately. The cut off of two study phases has been defined in reporting conventions [section 4.3](#). Listings of significant protocol deviations will be provided to support the summary tables.

7. Demographics and Baseline Characteristics

Demographics and baseline characteristics will be summarized by treatment group and total using the mITT population and safety population in the double-blind treatment phase and open-label safety population in the open-label extension phase. Individual subject listings will be provided to support the summary tables for all randomized subjects in the double-blind phase.

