9.1. Sarcoidosis Treatment Score (STS)

STS is a newly developed composite score that combines the results of PFT, chest imaging, quality of life, and changes in corticosteroid dosing. Individuals may score from - 6 to + 6. Higher scores indicate improvement. Subjects tolerating Acthar Gel (or placebo) will be categorized as Response, Partial Response, and Non Response. STS can be determined by using the assessments categories as presented in table below.

Table 1: Determining the Sarcoidosis Treatment Score

	Parameter	Improved	Unchanged	Deteriorate
Category of Assessment		+1	0	-1
PFT ^a	FVC	$\geq 5\%$	> -5% to < 5%	$\leq -5\%$
	DLCO	$\geq 5\%$	> -5% to < 5%	$\leq -5\%$
Imaging	HRCT	Improved	Unchanged	Worse
Quality of Life	King's Sarcoidosis Questionnaire (General Health)	≥ 4	> -4 to < 4	≤ -4
	Fatigue Assessment Score	≤ -4	> -4 to < 4	≥ 4
	Corticosteroid taper (dosage)	$\geq 50\%$ reduction	< 50% reduction or ≥ 5 mg increase for less than 2 weeks	≥ 5 mg increase for more than 2 weeks

^aAbsolute change of % predicted.

Subject tolerating Acthar (or placebo) will be categorized according the following scoring:

- Response is defined as scores of $\geq 3/6$ points.
- Partial Response is defined as scores of $2/6$ points or stable with corticosteroid reduction (ie, a total score of +1 due to $\geq 50\%$ reduction in corticosteroid dosage).
- Non Response is defined as scores of $\leq 1/6$ points without significant corticosteroid taper (stable or deterioration).

An STS responder is defined as a subject who has an assessed STS category of Response or Partial Response at 24 weeks (Visit 8) during double-blind treatment phase and at 48 weeks (Visit 11) during open-label phase.

The descriptive statistics for developed STS scores, number and percentage of subjects in each STS response category (response, partial response and non response) will be provided at both 24 weeks (Visit 8) and 48 weeks (Visit 11). At 24 weeks (Visit 8) during double-blind treatment phase, the proportions of STS responder (defined as response or partial response) and non-responder, and corresponding odds ratio will be calculated. The 95% confidence interval (CI) of the odds ratio will be calculated as well based on asymptotic method. Pearson's chi-square test (or Fisher's exact test if any expected count is less than 5) will be used to assess the comparability between treatment groups for the STS responder

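### The Week 24 STS responder rule gives no consequence to a prohibited or increased non-steroid antisarcoidosis drug, so a subject who improves on one can count as a responder

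*Protocol*

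**What the plan says.** **What is forbidden.** Protocol 10.2 states: "No new antisarcoidosis medication is permitted". It also bars anti-TNF treatment throughout the study. Protocol 10.1 says of other antisarcoidosis drugs: "The dose may be reduced or discontinued only for toxicity but must not be increased".

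**What follows if it happens.** Under 10.2 the use is recorded and "The designated study MM must be informed immediately so the sponsor may determine whether to continue the subject in the study". Protocol 17.1 requires stopping study drug in two situations, neither of them this one: "Discontinuation from IMP is mandated if the subject becomes pregnant or receives live or live-attenuated vaccines". Withdrawal for worsening is optional: "Subjects may be withdrawn if, in the opinion of the investigator, there is a lack of efficacy during the study".

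**How response is scored.** SAP 9.1: "An STS responder is defined as a subject who has an assessed STS category of Response or Partial Response at 24 weeks (Visit 8"). Response needs a total of at least 3. Partial Response needs a total of 2, or "a total score of +1 due to $\geq 50\%$ reduction in corticosteroid dosage". The six items are FVC, DLCO, HRCT, KSQ General Health, Fatigue Assessment Score and corticosteroid dose.

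**How the data are handled.** Efficacy uses the mITT population. Missing STS components are carried forward, and subjects who still cannot be classified become non-responders. The one STS sensitivity analysis uses observed data only. No per-protocol set is defined.

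**Where the drugs appear.** SAP 8.2 summarises concomitant sarcoidosis drugs by arm and phase. On deviations, SAP section 6 says: "The significant protocol deviations will be summarized by category using frequency tabulations based on the safety population", with supporting listings.

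**The concern.** The protocol treats added antisarcoidosis therapy as something that should not happen, but the endpoint ignores it when it does. Later improvement in lung function, imaging, quality of life or prednisone dose is credited to the randomised arm, whatever produced it. The score does penalise a sustained prednisone increase, so its treatment of added therapy is uneven: steroid escalation costs a point and non-steroid escalation costs none.

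At stake is the meaning of the Week 24 responder comparison, made at what both documents call the primary efficacy time point. As written, it mixes response to blinded treatment with response to blinded treatment plus a forbidden drug. The mix depends partly on case-by-case decisions about who stays in the study. No planned efficacy analysis separates the two.

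**Working it through.** The documents state no power, response rate or rate of prohibited use, so there is no planned figure to reproduce.

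**1. Three hypothetical subjects under SAP Table 1, items not mentioned unchanged**

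| Subject | Steroid item | Other five items | Total | Status |
|---|---|---|---|---|
| Prednisone up 5 mg for more than 2 weeks | -1 | 0 | -1 | Non-responder |
| Forbidden non-steroid drug; worsens, then returns to baseline | 0 | 0 | 0 | Non-responder |
| Forbidden non-steroid drug; prednisone halved | +1 | 0 | +1 | Partial Response, so responder |

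The drug itself enters no row. Only its effects do.

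**2. How open the route is**

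The other five items, each -1, 0 or +1, give 3^5 = 243 combinations. The numbers of combinations with sums 0, 1, 2, 3, 4 and 5 are 51, 45, 30, 15, 5 and 1.

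- Steroid item +1: responder if the other items sum to 0 or more. 51+45+30+15+5+1 = 147 of 243.
- Steroid item 0: responder if they sum to 2 or more. 30+15+5+1 = 51 of 243.
- Steroid item -1: responder if they sum to 3 or more. 15+5+1 = 21 of 243.

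The first count accepts any total of +1 that includes the steroid point. If all other items must be exactly unchanged, it becomes 45+30+15+5+1+1 = 97. These count score patterns and are not probabilities. They show that the route exists with or without the taper point.

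**3. Does any rule close the route?**

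- Sponsor decision (Protocol 10.2): may remove the subject, but need not.
- Early termination (Protocol 11.10): those who leave have Visit 8 procedures done, so values obtained on the added drug could still enter the score or its carry-forward.
- Non-responder imputation (SAP 9.1): triggered by missing data only.
- Adjudication (Protocol 8.1): described as addressing differences between raters; it gives no instruction on prohibited drugs.
- SAP section 6 and 8.2: descriptive only.

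**4. Size**

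SAP 4.1 gives 55 randomised, and the ratio is 1:1, so 55/2 = 27.5 per arm. The mITT set may be slightly smaller.

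- One such responder: 1/27.5 = 3.6 points in that arm (3.57 with 28 in the arm, 3.70 with 27).
- A net excess of 1 to 3 in one arm (assumed): 3.6 to 10.9 points on the difference, in either direction.

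More generally, let r be the share of an arm with such use and q the share of those users scored as responders. Compared with counting users as non-responders, the Acthar-minus-placebo difference shifts by q × (r_Acthar − r_placebo), taking q equal in both arms. All values below are assumptions.

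| r placebo | r Acthar | q | Shift (points) |
|---|---|---|---|
| 10% | 5% | 0.5 | -2.5 |
| 20% | 10% | 0.5 | -5 |
| 30% | 10% | 0.7 | -14 |
| 10% | 10% | any | 0 |
| 10% | 30% | 0.7 | +14 |

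**The case against.** **Treatment policy is a recognised choice.** Analysing outcomes whatever medication was added is legitimate in an mITT analysis, and the study is exploratory. This stands as far as it goes. The fault is that the plan neither states the choice nor shows the result without it. It is why the as-scored result should stay.

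**The route is narrow.** Scores measure change from baseline, so a subject who worsens and merely recovers scores 0. Protocol 11.3 ties tapering at Visit 3 to being improved or stable, and the taper algorithm figure is not shown. This stands: the added drug must produce a net gain, and taking it does not make a subject a responder.

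**There are other layers.** Independent adjudication overrides the investigator, and its criteria are not in these documents. SAP 8.2 would make an imbalance in added drugs visible by arm. Both are true. The first has no stated rule here, and the second does not alter the responder comparison.

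**Sections 10.1 and 10.2 differ.** The sponsor-discretion sentence concerns prohibited medication under 10.2, while dose increases are barred in 10.1. That distinction is fair, but no passage gives a consequence for an increase either.

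**A stronger reading.** A reader might infer that placebo subjects will be rescued more often, so that the placebo rate is inflated and a real effect hidden. That is plausible if the drug works, but nothing in the documents shows how often such drugs were used or in which arm.

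**Conclusion.** The gap is real. Under the plan as written, a subject who starts a prohibited antisarcoidosis drug, or has a background one increased, is scored with no consequence for that use and can be a Week 24 STS responder with a total of +2, or +1 through halved prednisone. A sustained prednisone increase costs a point, though even that does not bar responder status.

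Each such responder is worth about 3.6 points in an arm of about 27.5. The frequency, direction and total size of any bias are unknown, and every figure beyond the per-subject one rests on assumed rates. The documents do not support saying that the result is biased toward no effect, or that such subjects are common. They support saying that the responder analysis leaves a foreseeable event without a rule, in a trial small enough for a few subjects to matter. It should be fixed before unblinding.

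**What to change.** Add to SAP 9.1: for the Week 24 STS response, a subject who starts an antisarcoidosis treatment prohibited by Protocol 10.2, or has a background antisarcoidosis drug increased against 10.1, between first dose and Visit 8 is counted as a non-responder. Apply the same rule to the other double-blind responder endpoints, such as the FVC and DLCO improvement thresholds (SAP 9.3) and imaging improvement (SAP 9.4.1). Flag these subjects from the medication data, blind to arm, before unblinding.

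Report the as-scored (treatment-policy) result beside it, with the number of flagged subjects per arm, so the conclusion can be checked under both. The t-tests and MMRM for FVC and DLCO are not covered by this rule; one sentence should say that they use values regardless of added medication, if that is the intention.

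Clinical management of these subjects stays with the protocol. The cost is SAP wording, one flag from dates, doses and indications already collected under Protocol section 10, and one extra run per endpoint. Observed response rates may fall slightly in both arms.

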11. PROCEDURES

The schedule of study procedures is summarized in the Schedule of Events ([Table 1](#)).

If the subject is unable to come to the study site for any visit after the Baseline visit, all procedures that can be completed remotely (eg, by telephone) will be conducted as scheduled.

Collect as much information as possible, including but not limited to, AE information, new concomitant medications and changes in existing therapy, corticosteroid use, compliance with investigational therapy. Complete applicable physician assessments, PFT tests, subject-reported outcomes and assessments, 6MWT, ECG, imaging and laboratory tests at the next planned study visit as unscheduled procedures, if not already scheduled for that particular study visit.

Changes in study visit schedule, missed visits, and procedures will be captured in the eCRF.

11.1. Study Days -28 to -1 (Screening Visit 1)

Screening assessments must be performed within 28 days prior to Visit 2.

The following procedures will be performed at the screening visit:

- Informed consent. Neutral language should be used in describing the study to neutralized placebo effect.
- Injection and diary training. Subjects (or caregivers) will be trained on SC injections and diary completion using the training tools provided separately. The injection training may be foregone if either the subject or caregiver is a medically trained professional.
- Inclusion/exclusion criteria.
- Medical, surgical, and medication history. Medical history will include smoking history (classified into 1 the following categories: current smoker; ever smoked [more than 1 cigarette/day for more than 1 year]; never smoked), length of sarcoidosis diagnosis, organ involvement, and prior and current medication. Occupational history should also be collected.
- Demographics.
- Concomitant medications.
- Height.
- Vital signs. Vital signs will be obtained after the subject has been seated for 5 minutes (minimum) and will include systolic and diastolic blood pressures, pulse rate, and respiratory rate.
- Weight measured. Every effort should be made for weight to be measured by the same calibrated scale at every visit.
- Physical examination (see [Section 14.3](#)). The full physical examination will include a targeted examination of the organ(s) involved. All efforts must be undertaken for the same physician to perform the physical examination per subject, per organ involved, at each visit.

- Physician Global Assessment ([Attachment 7](#))
- ePOST.
- 12-Lead ECG (see [Section 14.6](#)).
- Patient-reported outcomes and assessments. Patient-reported outcomes include: Steroid toxicity questionnaire; King's Sarcoidosis Questionnaire ([Attachment 4](#)); Fatigue Assessment Scale ([Attachment 5](#)); Patient's Global Assessment ([Attachment 6](#)); Medical Research Council Dyspnea Scale ([Attachment 8](#)); Leicester Cough Questionnaire ([Attachment 9](#)), WPAI ([Attachment 10](#)) Prior to filling out any patient-reported outcomes at Visit 1, training will be provided as to the nature, purpose, and best way of filling these out. For example, reading the last question of the Fatigue Assessment Scale carefully.
- 6MWT: The 6MWT would be performed according to the ATS protocol ([Attachment 12](#)). Reasons for not performing the 6MWT will be captured in the eCRF.
- Clinical laboratory tests. Samples will be collected from subjects who have been fasted for at least 12 hours (drinking water is allowed). The following tests will be conducted:
 - Complete blood count.
 - Clinical chemistry (including liver function tests).
 - HbA1C.
 - Lipid profile.
 - 25-Hydroxy vitamin D and 1, 25-dihydroxy vitamin D, and parathyroid hormone.
 - C-reactive protein.
 - Thyroid stimulating hormone, thyroxine T3 and T4.
 - Hepatitis serology- Hepatitis B surface antigen, Hepatitis B core antibody, hepatitis C virus antibody, hepatitis C polymerase chain reaction for subjects positive for hepatitis C antibody only.
 - Biomarkers (including RNA and DNA, if genetic ICF signed).
 - Serum human chorionic gonadotropin hormone (females of child bearing potential only).
 - Urine analysis (local laboratory).
- Tuberculosis testing (tested by IGRA).
- PFT.
- CXR and HRCT should be performed within 28 days of Day -1. The CXR reading will also include Scadding scoring ([Attachment 11](#)).
- AEs (collected from the time of signature of the ICF).

- Contact IXRS to register subject.
- Schedule next visit and remind subjects to arrive in fasting condition for Visit 2 (drinking water is permitted).

11.2. Visit 2 Procedures

The investigator or designee will complete the following procedures at Visit 2:

- Inclusion/exclusion criteria review.
- Spirometry (ascertain any difference in FVC < 10% compared with FVC performed at Visit 1 before continuing).
- Vital sign determinations Vital signs will be obtained after the subject has been seated for 5 minutes (minimum) and will include systolic and diastolic blood pressures, pulse rate, and respiratory rate (see [Section 14.4](#)).
- Weight measured. Every effort should be made for weight to be measured by the same calibrated scale at every visit.
- Physical examination (see [Section 14.3](#)). The full physical examination will include a targeted examination of the organ involved. All efforts must be undertaken for the same physician to perform the physical examination (per organ involved) at each visit.
- ePOST: All efforts must be undertaken for the same physician to perform the ePOST ([Attachment 3](#)) side-by-side with prior evaluations.
- Physician Global Assessment ([Attachment 7](#)).
- Patient reported outcomes and assessments. Patient-reported outcomes include: Steroid toxicity questionnaire; King's Sarcoidosis Questionnaire ([Attachment 4](#)); Fatigue Assessment Scale ([Attachment 5](#)); Patient's Global Assessment ([Attachment 6](#)); Medical Research Council Dyspnea Scale ([Attachment 8](#)); Leicester Cough Questionnaire ([Attachment 9](#)), WPAI ([Attachment 10](#)).
- Clinical laboratory tests:
 - Complete blood count.
 - Clinical chemistry including liver function tests (samples will be collected from subjects who have been fasted for at least 12 hours. Drinking water is allowed).
 - HbA1C.
 - Human chorionic hormone (urine pregnancy testing, females of child bearing potential only [performed at a local laboratory]).
- Injection and diary training (if additional training is required).
- Contact IXRS to randomize subject and dispense study drug kits.
- Dosing will begin after Visit 2 procedures are completed and subject is randomized. Subjects (and/or caregivers) will be trained on SC injections and diary

completion using the training tools provided separately. Additional training may be provided during Visit 2 before randomization occurs. The injection training may be foregone if either the subject or caregiver is a medically trained professional. The subject or subject's caregiver will administer the first dose of IMP in the clinic under the supervision of study staff. The subject will remain in the clinic for at least 1 hour postinjection to monitor for allergic or anaphylactic reactions. Instruct the subject as to appropriate scheduling of weekly injections and the importance of compliance.

- AEs and concomitant medications.
- Remind the subject to return in fasting condition (drinking water is allowed) for the next visit and to bring all used and unused vials in a cooler. Subsequent visits should not be scheduled for the day of injection so as not to influence patient reported outcomes.

